**Exploratory Objectives:**

**Objective 1:** To estimate viral SARS-CoV-2 rebound rates (using the primary definition of viral SARS-CoV-2 rebound), prior to the Omicron era and during the Omicron era, in high frequency (volume) SARS-CoV-2 diagnostic testers (using the primary definition of high frequency testing), among those treated with Paxlovid/nirmatrelvir-ritonavir for SARS-CoV-2 versus those with no evidence of SARS-CoV-2 treatment (untreated) for SARS-CoV-2, stratified by:

- a. Demographics of participants
- b. Time from first positive test to treatment (if treated).

- c. Participants at high-risk for progression to severe SARS-CoV-2 versus those not at high-risk, if sample size allows. If sample size is limited, age (<50 years of age versus 50+ years of age) will be used as a proxy for high-risk for progression to severe SARS-CoV-2 status)
- d. Co-infections
- e. Vaccinated against SARS-CoV-2 (has received at least 1 dose) and time since last vaccine dose > 6 months vs. ≤ 6 months
- f. Multiple SARS-CoV-2 treatment prescription status

**Objective 2:** To examine risk factors and clinical outcomes of viral SARS-CoV-2 rebounders (using the primary definition of viral SARS-CoV-2 rebound), prior to the Omicron era and during the Omicron era in high frequency (volume) SARS-CoV-2 diagnostic testers (using the primary definition of high frequency testing), among those treated with Paxlovid/nirmatrelvir-ritonavir for SARS-CoV-2, those untreated for SARS-CoV-2 versus those with no evidence of SARS-CoV-2 treatment (untreated) for SARS-CoV-2, as defined below:

- a. Risk factors
  - i. High-risk factors
  - ii. Demographics
  - iii. Other risk factors to be determined
- b. Clinical outcomes, based on healthcare utilization during follow-up post-index date
  - i. Hospitalization (including length of stay)
  - ii. Hospitalizations with invasive mechanical ventilation
  - iii. Emergency room visits
  - iv. Urgent care visits
  - v. All-cause mortality

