### **9.2.2. Time periods**

#### **9.2.2.1. Study period**

The study will include an overall study period of June 01, 2020, to February 28, 2023.

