#### **9.2.2.4. Follow-up**

The follow-up period starts at index date and participants will be followed until the date of the first occurring of the following events:

- Death
- At the end of their database disenrollment from the database
- At the end of study period
- Occurrence of the outcome/endpoint of interest

Further details will be defined in SAP.

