## Endpoints

The following are the primary endpoint:

- Viral SARS-CoV-2 rebound\*, where the main definition defines rebound as 1.) a positive test (at the index date), followed by a single negative test, followed by a positive test - within 28 days, or 2.) 1 or more positive tests starting at the index date, followed by 1 or more negative tests, followed by a positive test within same 28-day time span. Index date will be defined as first positive test date.

The following are the exploratory endpoints:

- Clinical outcomes (within 30 days of index date), based on healthcare utilization following viral SARS-CoV-2 rebound
  - Hospitalization (including length of stay)
  - Hospitalizations with invasive mechanical ventilation
  - Emergency room visits
  - Urgent care visits
  - All-cause mortality

\*Alternate definitions of viral SARS-CoV-2 rebound will be included in sensitivity analyses and detailed in the SAP.

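### Exploratory clinical outcomes must follow rebound but are counted only to day 30 from index, leaving 2 to 28 days at risk; Section 8 counts the same outcomes from index

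*Supplement*

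**What the plan says.** Section 9.4 (Endpoints) gives the exploratory outcomes as "Clinical outcomes (within 30 days of index date), based on healthcare utilization following viral SARS-CoV-2 rebound", and lists hospitalization, ventilated hospitalization, emergency room visits, urgent care visits and all-cause mortality. The same section fixes the clock: "Index date will be defined as first positive test date". Rebound itself is either "a positive test (at the index date), followed by a single negative test, followed by a positive test - within 28 days" or one or more positives "followed by 1 or more negative tests, followed by a positive test within same 28-day time span".

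Section 9.2.2.4 says "The follow-up period starts at index date" and lists death, disenrollment, end of study and "Occurrence of the outcome/endpoint of interest" as reasons for follow-up to end. It leaves further detail to the SAP, which is not among the documents.

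Exploratory Objective 2b in Section 8 describes the same five outcomes as "Clinical outcomes, based on healthcare utilization during follow-up post-index date". It sets neither a 30-day limit nor a condition that the event come after rebound.

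**The concern.** The Section 9.4 definition has a start that moves with the patient (the rebound test) and an end that does not (day 30 from the first positive). Two patients with the same risk after rebound are watched for very different lengths of time only because one rebounded later. A simple percentage with an event then mixes risk with length of observation, and it always errs toward too few events.

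The Section 8 wording errs the other way. A patient admitted on day 3 who rebounds on day 20 has an outcome under Section 8 and none under Section 9.4. An analyst could defend either result, and they answer different questions.

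Section 7 designates this a post-authorization safety study, and these are the only endpoints listed that address the clinical consequences of rebound. A definition that under-counts such events should therefore be mended even at exploratory level.

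**Working it through.** The protocol states no event rate, sample size or power for these outcomes, so there is no figure to reproduce. The check is on time at risk.

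**Inputs.** Window end: day 30 from index (Section 9.4). Latest rebound: day 28 (Section 9.4). Earliest rebound: day 2 (positive day 0, negative day 1, positive day 2), assuming at most one test a day; the protocol sets no minimum gap. Tester rule: at least 3 tests within 28 days and a median gap of at most 10 days (Section 9.3.1).

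**Days at risk after rebound** = 30 − rebound day.

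| Rebound day | Days left | Share of a 30-day window |
|---|---|---|
| 2 | 28 | 93% |
| 9 | 21 | 70% |
| 14 | 16 | 53% |
| 20 | 10 | 33% |
| 28 | 2 | 7% |

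The spread is 28/2 = 14-fold. Day 9 is shown because Section 7 cites it as a median time to symptom rebound in another patient group. It is an illustration, not an estimate for this cohort.

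**Does the tester rule narrow the range?** With exactly three tests there are two gaps, and their median is their mean. So (g1 + g2)/2 ≤ 10 gives g1 + g2 ≤ 20, and rebound comes by day 20 at the latest, with 10 days left. With four tests the median is the middle gap: tests on days 0, 9, 18 and 28 have gaps 9, 9 and 10, median 9, and qualify. Listing all patterns of 4, 5 and 6 tests confirms that day 28 stays possible. The range of 2 to 28 days stands for the cohort, but its lower end needs four or more tests.

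**Size of the under-count (illustration).** Assume a constant hazard h and no effect of rebound on risk. With 30-day risk p, h = −ln(1 − p)/30, and the risk captured after a rebound on day t is 1 − exp(−h(30 − t)). For p = 5% and t = 9: h = 0.00171, captured risk 3.53%, ratio to the full 30-day risk 0.705. For p from 0.5% to 10%:

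- all rebounds on day 9: ratio 0.70 to 0.71
- rebound days uniform over 2 to 20 (mean 19 days left): 0.63 to 0.64
- rebound days uniform over 2 to 28 (mean 15 days left): 0.50 to 0.51

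With a fixed 30 days from rebound the ratio is 1.00 in every case.

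**Treatment contrast.** If both groups rebound on the same days, they lose the same time. If the means differ, say day 14 against day 9 (assumed), the ratio of time at risk is (30 − 14)/(30 − 9) = 16/21 = 0.76 with no true difference. This feeds directly into a comparison of proportions. It also feeds into a Cox model with time zero at index, as Section 9.2.2.4 implies, unless patients enter the risk set only at rebound. A Cox model with time zero at rebound would treat day 30 as censoring and largely avoid it, but the protocol does not set that origin.

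**The case against.** The strongest case against is that this is only a wording conflict. Both sections anchor on index. If Section 9.4 means 30-day use from index among patients who rebound, no window shrinks. The endpoints are exploratory, the study is descriptive with no hypotheses (Section 9.6), follow-up detail is left to the SAP, and no document gives the distribution of rebound days, so the actual loss is unknown. Much of this is fair. The under-count and the crediting of pre-rebound events belong to different readings and cannot both occur. But the 30-day-from-index window and the requirement that use follow rebound both stand in the protocol, and the Section 9.4 footnote on endpoints defers only alternate rebound definitions. Programming Section 9.4 faithfully produces the unequal exposure.

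A reader might infer three stronger points, which the documents do not support:

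- *Rebounders carry immortal time and will look healthier than non-rebounders.* Exploratory Objective 2 concerns rebounders by treatment and names no non-rebounder group. Sections 9.2.2.3, 9.3.1 and 9.4 place index inside a positive-negative-positive sequence, so the cohort, read literally, has no non-rebounders. Any who were admitted would also have to survive and keep testing to reach three tests. Section 9.8 plans models of risk factors and outcomes for rebound, which is ambiguous, so this bias is conditional on a comparison not clearly planned.
- *Section 9.2.2.4 closes follow-up at rebound.* The phrase is ordinarily read per outcome: in a hospitalization analysis, hospitalization ends follow-up. One clarifying sentence suffices.
- *Late index dates must be dropped because follow-up is incomplete.* Section 9.2.2.4 already censors at study end and Section 9.8 plans Cox models, which accommodate it.

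**Conclusion.** The point holds for the exploratory clinical outcomes. As Section 9.4 is written, observation after rebound lasts between 2 and 28 days according to the rebound day (10 to 28 for patients with exactly three tests), and absolute post-rebound risk is understated. Under a constant hazard with assumed rebound timings, roughly 50% to 71% of the full 30-day risk would be captured. The loss would be smaller if events cluster just after rebound. The Paxlovid versus untreated contrast is distorted only if time to rebound differs by treatment and the analysis does not start its clock at rebound. Sections 8 and 9.4 conflict on whether events before rebound count.

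It would go too far to say the study will find rebound harmless by design: the rebound-day distribution is unknown and the analysis detail is deferred. The primary rebound estimate is not affected. The change is worth making, at a weight that suits exploratory endpoints.

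**What to change.** In Section 9.4, define each clinical outcome as the first event within a fixed 30 days after the rebound-positive date, with time zero at that date and censoring at disenrollment or study end. Report the 30-day risk by a method that uses the censoring. Reword Exploratory Objective 2b in Section 8 to match. If use from index is also wanted, list it as a separate outcome and do not describe it as following rebound.

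In Section 9.2.2.4, state that rebound ends follow-up only for the rebound endpoint.

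If Section 9.8 is meant to compare rebounders with non-rebounders, say so. Then treat rebound as a time-dependent covariate, or match each rebounder to patients still event-free on the same day since index and start both clocks there.

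The cost is wording in three or four places, slightly more programming, and censored follow-up for patients who rebound after 29 January 2023 (30 days before the study ends on 28 February 2023). No earlier cut-off for index dates is needed.

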## Covariates

Covariates will include baseline demographic, high-risk clinical characteristics (comorbidities) for progression to severe SARS-CoV-2, medications, and health utilization, as well as those needed for the study cohort inclusion and exclusion criteria. These are not intended to be the exclusive lists. Adjustments of the covariates may be made, and additional variables may be added in SAP as needed over time. The code lists of conditions and medications (if applicable) will be provided in SAP.

*Demographics (prior to index date):*

- Age/Age group (age groups to be defined in the SAP)
- Gender
- Race/ethnicity (if available)
- Location/region (if available)

*High-risk clinical characteristics (comorbidities) for progression to severe SARS-CoV-2 (prior to index date):*

- Immunosuppressive disease or immunosuppressive treatment.
- Cancer (active) other than localized skin cancer
- Cardiovascular conditions (Cerebrovascular disease or stroke, coronary heart disease, cardiomyopathies, heart failure, etc.)
- Chronic kidney disease (CKD)
- Deyo-Charlson Comorbidity Index Score
- Diabetes mellitus
- HIV
- Hypertension

- Chronic liver disease (cirrhosis; non-alcoholic fatty liver disease; alcoholic liver disease; autoimmune hepatitis, etc.)
- Neurodevelopmental disorders
- Obesity
- Respiratory conditions (Asthma, Chronic obstructive pulmonary disease (COPD), Interstitial lung disease (ILD), Chronic lung disease, etc.)
- Sickle cell disease
- Smoking status (current or former)

*Prior healthcare characteristics (prior to index date):*

- Prior-year healthcare utilization
- Prior SARS-CoV-2 infection/s
- Prior SARS-CoV-2 vaccination/s (never vaccinated,  $\geq 1$  dose with most recent dose given within 6 months of index date,  $\geq 1$  dose with most recent dose  $>6$  months from index date)
- Prior influenza vaccinations

*Risk factors to be examined (prior to index date):*

- All demographics, high-risk clinical characteristics (comorbidities) for progression to severe SARS-CoV-2 and prior healthcare characteristics mentioned above

*Diagnostic Testing Characteristics (on or after index date):*

- High frequency (volume) SARS-CoV-2 diagnostic testing status\*\*

*Medications for treatment of COVID-19 (on or after index date):*

- Anti-SARS-CoV-2 Monoclonal Antibodies
  - Bamlanivimab/Etesevimab
  - Casirivimab/Imdevimab
  - Sotrovimab
  - Tixagevimab/Cilgavimab
  - Bebtelovimab
- Antiviral therapy
  - Paxlovid/nirmatrelvir-ritonavir
  - Lagevrio/molnupiravir
  - Veklury/remdesivir [IV]

\*\*Alternate definitions of high frequency (volume) SARS-CoV-2 diagnostic testing will be included in sensitivity analyses and detailed in the SAP.

## 9.5. Data sources

This study will be conducted using SARS-CoV-2 diagnostic testing data from the Helix Respiratory Registry with linkage to the retrospective Komodo Healthcare claims data during the period of

01 June 2020, to 28 February 2023, after appropriate de-identification certification, data privacy, and security compliance in accordance with Pfizer and Helix policies and industry best practices.

## 9.6. Study size

This is a descriptive study with no minimum sample size. All eligible participants during the relevant study periods will be included. This is a NI study with no a priori hypotheses specified; therefore, sample size calculations are not applicable.

Preliminary feasibility counts provided to Pfizer, Inc. by Helix indicate that 1,244,791 SARS-CoV-2 diagnostic tests performed from 10 October 2020, to 10 August 2022, among individuals who have tested with a Helix SARS-CoV-2 diagnostic test through a retail pharmacy in the US, 558,340 of these tests were positive. These positive tests represent 449,759 unique infections, defined as positive tests more than 28 days apart. Among high frequency (volume) SARS-CoV-2 diagnostic testers (under the primary definition), there were 21,991 unique infections during the same time period.

## 9.7. Data management

All data exists as structural data originating from two sources; part one from Helix's Respiratory Registry database (AWS Redshift), and the second part from Komodo's insurance claim database (Snowflake). Both datasets are routinely deidentified via Datavant's tokenization solution. Helix's dataset is version controlled on both the extraction date and the extract transform load (ETL) code side. Extracted flat files used for encrypted transit into Komodo's environment Sentinel are furthermore integrity tested by checksums (SHA256 and AWS ETag) and scanned for sensitive data before ingested into a study-specific Snowflake SQL (v6.41.2) environment. A concatenated ID string based on Datavant's tokens 1 and 2 is used for joining the two datasets throughout the study. Further data will be added by either vendor's data analytics team as needed or in case of relevance. As the database will be regularly updated, date and version of the database will be specified in the report of the study.

Originating data from Helix are under Helix's data management policies and procedures, developed by Helix's information and security teams. Data at Helix is stored following industry best practices. Following implemented comprehensive physical, organizational, technical, and administrative controls to ensure that data collection, storage, and use of directly identifiable information adheres to stringent security requirements and complies with applicable law, in accordance with Health Insurance Portability and Accountability Act (HIPAA) and National Institute of Standards and Technology (NIST) standards.

The study will be conducted by the analytic team at Helix. Personalized credentials will be used by each member of the Helix team for security and audibility when accessing the Sentinel environment. Retention of study-related data, documents, and other materials will be governed by Pfizer Policy on Records and Information Management, and per this policy, will remain effective for a period of five years from the date of project initiation. Amendments must be made only with the prior approval of Pfizer.

## 9.8. Data analysis

Descriptive statistics among individuals with SARS-CoV-2 in the Helix Respiratory Registry that overlap with the retrospective Komodo Healthcare claims data will be summarized. Means with standard deviations, medians with interquartile ranges will be provided for continuous variables. Numbers and percentages will be provided for dichotomous variables or categorical variables.

For exploratory analyses, logistic regression or Cox proportional hazards regression models will be used to identify risk factors and outcomes for viral SARS-CoV-2 rebound in adjusted analyses. Model selection will balance biological and contextual knowledge for potential confounders with statistical considerations for model fit and the bias versus variance tradeoff.

An analysis comparing viral SARS-CoV-2 rebound, between participants treated with Paxlovid, untreated participants (and pending sufficient sample size, comparator SARS-CoV-2 treatment group(s) described above) will be conducted. Viral SARS-CoV-2 rebound and other outcomes in participants who received Paxlovid compared with untreated participants (and/or comparator SARS-CoV-2 treatment group(s), pending sufficient sample size) will be evaluated using multivariable Cox regression models with propensity score inverse probability of treatment weighting (IPTW) with a robust variance estimator having age, sex, week and year of initial positive SARS-CoV-2 test, and potentially the aforementioned baseline clinical characteristics and comorbidities as independent variables to account for time-varying confounding. Standardized mean differences (SMDs) will be calculated to check whether IPTW yielded comparable cohorts, considering an SMD below 0.1 as indicating satisfactory covariate balance.

Detailed methodology for summary and statistical analyses of data collected in this study will be documented in a statistical analysis plan (SAP), which will be dated, filed, and maintained by the sponsor. The SAP may modify the plans outlined in the protocol; any major modifications of primary endpoint definitions or their analyses would be reflected in a protocol amendment.

## 9.9. Quality control

Analyses are programmed according to the specifications in the protocol, and the SAP, and documented in a programming plan as appropriate. Data imported into Komodo's environment Sentinel from Helix is processed by an ETL codebase developed following an industry best practices approach. Including, test-driven development with unit/integration tests and a software development lifecycle, which includes source control and reviewed pull requests. Data integrity controls are performed by checksums (SHA256 and AWS ETag) during and after an encrypted transfer between Helix and Komodo's platforms. Final deliverables will be reviewed and verified by a second, independent programmer who may also perform double programming. All quality checks will be documented in the programming plan.

## 9.10. Limitations of the research methods

COVID-19 is a new disease with evolving diagnostic testing, disease mechanisms and treatments. Many infected persons are thought to have mild to unrecognizable symptoms and may therefore not present for testing. Thus, participants with these infections will not be identifiable in the datasets, especially if they did not undergo repeated diagnostic testing for SARS-CoV-2. However, as high-

volume repeat testers are more likely to undergo a positive-negative-positive test pattern, which will result in an overestimate of the true proportion of participants who experience viral SARS-CoV-2 rebound (along with SARS-CoV-2 treatment rebound (including Paxlovid)) as the worst-case scenario, yet these results should form a conservative upper-limit estimate.

Participants with chronic diseases or in inpatient settings, the elderly, or other risk groups may be more likely to be under ongoing care or thought to be at higher risk and therefore may be more likely to seek care or be referred for testing. Differences among at-risk subpopulations may arise from access to care/health care seeking behaviors rather than true differences in risk. Generalizability may be limited as SARS-CoV-2 testing patterns and treatment are evolving over time, and health care seeking behaviors among participants at high-risk of SARS-CoV-2 progression may differ from those who are not at high-risk .

Additional limitations are similar to those from observational studies, including the inability to obtain detailed clinical information on disease severity and activity due to the nature of secondary databases. However, the Komodo Healthcare claims data provides a more accurate record of all prescriptions given compared to electronic health records (EHRs), which it is able to indicate whether or not a prescription is filled, including refills. Being able to access this additional component provides the opportunity to calculate additional measures (e.g., if refills were filled on time). Finally, there is a lack of complete similarity between the criteria used to construct the high-risk subcohort in this study and the high-risk criteria implemented in the EPIC-HR clinical trial.

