Post-treatment increases in SARS-CoV-2 RNA levels (i.e., viral RNA rebound) in nasopharyngeal samples were observed on Day 10 or Day 14 in a subset of nirmatrelvir/ritonavir and placebo recipients in the EPIC-HR study. The frequency of detection of post-treatment viral RNA rebound varied according to analysis parameters but was generally similar among nirmatrelvir/ritonavir and placebo recipients, regardless of the rebound definition used. For participants who showed a half- $\log_{10}$  or greater increase relative to end of treatment and whose viral load was persistent through follow-up, the occurrence was 1.73% placebo and 2.32% nirmatrelvir/ritonavir. In addition to these, some participants had transient half- $\log_{10}$  or greater increases relative to end of treatment, the occurrence was 2.35% in placebo vs 4.65% nirmatrelvir/ritonavir. A similar or smaller percentage of placebo recipients compared to nirmatrelvir/ritonavir recipients had nasopharyngeal viral RNA results <LLOQ at all study timepoints in both the treatment and post-treatment periods. Post-treatment viral RNA rebound was not associated with the primary clinical outcome of COVID-19-related hospitalization or death from any cause through Day 28 following the single 5-day course of nirmatrelvir/ritonavir treatment. Post-treatment viral RNA rebound also was not associated with drug resistance as measured by mPro sequencing. The clinical relevance of post-treatment increases in viral RNA following nirmatrelvir/ritonavir or placebo treatment is unknown.

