In response to the COVID-19 pandemic, Helix OpCo (Helix), an accredited laboratory (CAP #9382893, CLIA #05D2117342) based in San Diego, CA, with a suite of laboratory capabilities to support infectious disease programs and public health surveillance (including SARS-CoV-2 / Flu diagnostic testing, SARS-CoV-2 whole genome sequencing, and pan-respiratory virus whole genome sequencing), developed laboratory capabilities to support SARS-CoV-2 diagnostic testing. With funding from the NIH's Rapid Acceleration of Diagnostics (RADx) program, Helix became a national "mega-lab" for processing up to 150,000 SARS-CoV-2 real-time reverse transcription polymerase chain reaction (rRT-PCR) diagnostic tests per day. Helix also has partnered with the CDC to provide SARS-CoV-2 whole genome sequencing starting in December 2020 and continues to support public health sequencing efforts. Helix has processed over ten million SARS-CoV-2 RT-PCR diagnostic tests and hundreds of thousands of SARS-CoV-2 whole genome sequences. Helix has established registries, biorepositories, and Institutional Review Board (IRB) protocols for both human genomics and viral genomics programs, enabling performance of research initiatives and key analyses to inform public health decision-making.

In this study, we will leverage Helix's existing US-based Respiratory Registry (External Protocol #0003-0001) of in vitro diagnostic rRT-PCR testing for the qualitative detection of nucleic acid in anterior nasal swab specimens for the detection of the SARS-CoV-2 and Influenzas A/B with linkage to retrospective Komodo Healthcare claims data in order to further examine viral SARS-CoV-2 RNA rebound (SARS-CoV-2 rebound) patterns. Specifically, viral SARS-CoV-2 rebound will be examined after stratification of variables such as SARS-CoV-2 therapeutic treatment, viral load patterns, co-infections, and by timing around rebounds in relation to initial test positivity to treatment for SARS-CoV-2.

This non-interventional study (NIS) is designated as a Post-Authorization Safety Study (PASS) and is conducted voluntarily by Pfizer.

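### Section 9.10 calls the rebound rate a conservative upper limit after weighing only upward bias; the design also under-counts rebounds, so the net direction is not established.

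*Supplement*

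**What the plan says.** Protocol section 9.10 gives one reason for the direction of bias: "volume repeat testers are more likely to undergo a positive-negative-positive test pattern, which will result in an overestimate of the true proportion". It extends this to rebound after treatment, with Paxlovid named, describes the result as the worst case, and ends: "yet these results should form a conservative upper-limit estimate".

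Other sections fix what can be counted:

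- Section 9.4 (Endpoints) defines primary rebound as "a positive test (at the index date), followed by a single negative test, followed by a positive test - within 28 days", or one or more positives "followed by 1 or more negative tests, followed by a positive test within same 28-day time span". Both forms need a negative in between.
- Section 7 describes the assay as "qualitative detection of nucleic acid in anterior nasal swab specimens".
- Sections 9.2 and 9.5 take test results from the Helix registry. Komodo supplies claims.
- Section 9.3.1, item 2, admits people with at least three tests in 28 days and a median gap of at most 10 days.
- Primary Objective 1 (section 8) and the index date (9.2.2.3) admit only people who already have a positive-negative-positive sequence.
- Secondary Objective 3 (section 8) uses a looser rebound definition: two positives more than 14 days apart.

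**The concern.** An upper limit needs the net bias to be upward. Section 9.10 names no force that lowers the rate and does not argue that the upward one dominates. Yet other sections build in under-counting.

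The study is designated a PASS (section 7), and the Annex 1 abstract treats rebound as the safety event of interest. If the wording reaches the report, readers may take the observed rate as a ceiling on risk, including after Paxlovid. If that ceiling is wrong, it errs towards reassurance.

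**Working it through.** The plan gives no rebound rate or numerical bound to reproduce. The check therefore compares sections and adds two illustrations on assumed inputs.

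**1. Rebounds that never turn negative.** The EPIC-HR background in section 7 counts a half-log10 "or greater increase relative to end of treatment and whose viral load was persistent through follow-up", and separately transient rises of the same size. Neither needs a negative. On a positive/negative readout, someone who stays positive while viral load falls and rises is not a primary-endpoint rebound.

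**2. Test spacing.** The 10-day cap is on the median. With three tests there are two gaps and the median is their mean, so gaps of 4 and 16 days also qualify. Take rebounds that do have a negative phase of w days, then a positive phase of r days, with tests every g days at a random offset. For g ≥ w the sequence is seen with probability max(0, min(w, w + r − g))/g. For shorter gaps it is always seen if r ≥ g. Assume w = 2 to 5 and r = 5 to 7, with the negative phase starting on day 5 to 10 (latest end 10 + 5 + 7 = day 22, inside 28 days):

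| g (days) | Lowest | Highest |
|---|---|---|
| 3 | 2/3 = 67% | 100% |
| 5 | 2/5 = 40% | 100% |
| 7 | (2+5−7)/7 = 0% | 5/7 = 71% |
| 10 | 0% | (5+7−10)/10 = 20% |

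**3. Helix-only results.** No section says that home or other-laboratory results are captured. If the negative or the second positive was obtained elsewhere, a true rebound counts as a non-rebound, but only if the person still has three Helix tests. Otherwise the person leaves numerator and denominator together.

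**4. Net direction under the three-test cohort.** Let p be the true rebound proportion, k the enrichment of rebounders among frequent testers, s the share of true rebounds seen as positive-negative-positive in Helix data, and f the share of non-rebounders showing that pattern falsely. Then

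observed = k·p·s + (1 − k·p)·f.

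The documents give none of k, s and f, so these are assumptions. For p, I add the EPIC-HR persistent and transient figures, assuming the groups are separate: placebo 1.73 + 2.35 = 4.08%; nirmatrelvir/ritonavir 2.32 + 4.65 = 6.97%.

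| k | s | f | Observed, p = 4.08% | Observed, p = 6.97% |
|---|---|---|---|---|
| 1 | 0.3 | 1% | 2.18% (below) | 3.02% (below) |
| 1.5 | 0.4 | 1% | 3.39% (below) | 5.08% (below) |
| 2 | 0.4 | 1% | 4.18% (above) | 6.44% (below) |
| 2 | 0.8 | 1% | 7.45% (above) | 12.01% (above) |
| 3 | 0.8 | 2% | 11.55% (above) | 18.31% (above) |

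For example, with k = 1.5, s = 0.4, f = 0.01: 0.10455 × 0.4 + 0.89545 × 0.01 = 0.0508. The table shows only that the sign depends on unknown inputs. It does not estimate the bias.

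**5. The other cohort reading.** If the tester definition of Primary Objective 1 and the index date of 9.2.2.3 are applied literally, every member has the endpoint and the rate is 100%. The three-test reading needs item 2 of 9.3.1 together with the sentence in 9.4 that sets the index date at the first positive test. Item 1 of 9.3.1 again ties the index date to the full sequence.

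**The case against.** **The endpoint is a definition.** The protocol chose positive-negative-positive, and a half-log10 RNA rise is a different construct. Section 7 itself says frequency varied with analysis parameters. This has weight against calling the endpoint wrong. But 9.10 speaks of overestimating a true proportion, so it claims something beyond the observed pattern. Spacing and Helix-only capture also lose rebounds that do meet the protocol's own definition.

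**Secondary Objective 3 needs no stated negative.** True, and it is partial cover. It misses second positives within 14 days and keeps the primary tester definition, which in section 8 itself requires the negative. It leaves the wording of 9.10 unchanged.

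**The SAP may add definitions.** No SAP is shown, and it may. The inference in 9.10 is nevertheless complete as it stands in the protocol.

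**The upward bias is real.** It is, and false negatives within a continuing infection add to it. A reader might infer that the figure bounds nothing, or that it is too low. The documents support neither: part of the range above lies over the true rate.

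**Two further inferences to avoid.** A reader might suppose that patients too ill to return to a pharmacy are lost. The documents offer no support, and the case review in section 7 describes rebound symptoms as mild. Nor is retail-pharmacy testing an eligibility rule. It appears in the title and in the feasibility counts of 9.6, which describe "individuals who have tested with a Helix SARS-CoV-2 diagnostic test through a retail pharmacy in the US".

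**Conclusion.** The concern holds as a point about an unsupported inference. Under the three-test cohort, the primary rebound rate carries upward and downward biases whose balance the documents do not establish, so it has not been shown to be an upper limit, overall or in Paxlovid recipients. Under the positive-negative-positive cohort it is 100% by construction, which bounds the risk but says nothing about it.

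The size cannot be fixed from the documents. The illustrations rest on assumed values of k, s, f, w and r, and on adding the two EPIC-HR figures. The conclusion needs only the definitions themselves and the absence of any argument in 9.10 that the upward force prevails.

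**What to change.** 1. In 9.10, remove the worst-case and upper-limit phrases. State instead that the rate is the proportion of repeat testers with a registry-observed positive-negative-positive sequence, that it may over- or under-estimate rebound risk, and that it has not been shown to be an upper bound, overall or among Paxlovid recipients.
2. List the under-counts there: rebounds that never turn negative, negative phases missed between tests, and results from outside Helix among people who still have three Helix tests. Note that Secondary Objective 3 covers the first only in part.
3. Keep upper-bound wording out of the study report and publications.
4. Reconcile the cohort and index-date definitions in section 8 (Primary Objective 1), 9.2.2.3, 9.3.1 and 9.4, and in the Annex 1 abstract.
5. Optional, only if cycle-threshold values are held: count patients with consecutive positives and a later fall in cycle threshold, to help size the first under-count. Section 7 mentions viral load patterns, but no section says such values are available.

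Items 1 to 3 cost only wording, and the stated conclusion becomes less favourable. Item 4 needs a decision on the denominator and, if it changes the primary analysis, an amendment under 9.8. Item 5 would use stored data.
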